13.1 Reporting to the NIH IRB

UPs, non-compliance, and other reportable events will be reported to the NIH IRB according to HRPP Policy 801.

13.2 Reporting to the NIAMS Clinical Director

The principal investigator will report UPs, major protocol deviations, and deaths to the NIAMS clinical director according to institutional timelines.

14 Clinical Monitoring Structure

To help ensure that NIH Office of Research Support and Compliance procedures and Good Clinical Practices are being carried out, a Clinical Trials Management designee within the Office of Clinical Research Policy and Regulatory Operations, Regulatory Compliance and Human Subjects Protection Program will conduct a study initiation visit before study enrollment begins. The purpose of this meeting is to review with the principal investigator and study team designees the roles and responsibilities concerning their commitment to adhere to the requirements of the protocol, especially in terms of NIH Office of Human Subjects Research Protections reporting requirements for reportable events. In addition, the quality management and data management plan for the study will be reviewed.

14.1 Quality Management Plan

During the study, the principal investigator and study team will be responsible for implementing a quality management plan. Additionally, the study team will be responsible for completing and submitting a summary report on the quality plan to the NIAID clinical director or designee at least annually as detailed in the quality management plan. A courtesy copy will also be sent to Clinical Trials Management.

14.2 Safety Monitoring Plan

The NIAID intramural DSMB includes independent experts that do not have direct involvement in the conduct of the study and have no significant conflicts of interest as defined by NIAID policy. The DSMB will review the study protocol and informed consent document prior to initiation and twice a year thereafter, or as may be determined by the DSMB.

The DSMB may convene additional reviews as necessary. The DSMB will review the study data as needed to evaluate the safety, efficacy, study progress, and conduct of the study.

All deaths, SAEs, and UPs will be reported to the DSMB at the same time they are submitted to the IRB unless otherwise specified herein.

The principal investigator will notify the DSMB at the time halting criteria are met and obtain a recommendation concerning continuation, modification, or termination of the study. The principal investigator will submit the written DSMB summary reports with recommendations to the IRB.

15 Statistical Considerations

15.1 Definition of the Study Endpoints

The primary endpoint of this study is a list of human protein-coding genes and non-coding RNAs (small RNAs and long non-coding RNAs) that are differentially expressed in response to glucocorticoids in patients with SLE, for each of the studied cell types and doses.

The secondary endpoints of this study are:

1. A comparison of the transcriptional response to glucocorticoids between the 2 dose groups.
2. A list of protein-coding and non-coding transcripts, their corresponding proteins, and molecular pathways representing the best candidates for targeted therapeutic alternatives to glucocorticoids.
3. Validation of the targets identified by functional studies.
4. For each cell type, a list of protein-coding or non-coding transcripts that are shared and a list of transcripts that are different, between patients with SLE and the previously studied healthy controls, at baseline or in response to glucocorticoids.

15.2 Bioinformatics Pipeline and Data Handling

The output of the RNA and small-RNA sequencing runs (bcl files) will be converted to FASTQ format with the software program bcl2fastq. Quality control of the resulting FASTQ files will be performed with the software program FastQC. RNA-seq data will be aligned to the most recent human genome assembly using the software program STAR.⁴⁴ The resulting BAM files and the most recent version of the GENCODE will be used to obtain raw read counts for each transcript, with the featureCounts program of the package Subread.⁴⁵

15.3 Identification of Glucocorticoid-responsive Genes

To identify glucocorticoid-responsive genes, differential expression analysis for the RNA-seq and small-RNA-seq data will be performed in R, with the package DESeq2.⁴⁶

For each cell type, we will assess the level of variation in the baseline measurements by comparing the expression values on the day of the screening visit to the 0-hour (pre-infusion) values on the day of the glucocorticoid infusion. For participants who undergo a glucocorticoid taper, this analysis will contrast the pre- and post-taper patterns of gene expression. We will then perform differential analysis comparing each of the two post-infusion time points (2 hours and 4 hours) independently against the baseline. DESeq2 (section 15.6) adopts the method of Benjamini-Hochberg to adjust for multiplicity. We will draw conclusions based on the Benjamini-Hochberg adjusted p values, which control for the family-wise false discovery rate (FDR) in the presence of multiple comparisons. We will employ a cutoff FDR⁴⁷ value of < 5% to

select the transcripts that will be considered differentially expressed in each cell type at each time point. The resulting gene lists will be contrasted to determine, for example, which genes are uniquely differentially expressed in a specific cell type, or common to a specific hematopoietic lineage. They will also be used for pathway enrichment analysis, to determine the molecular pathways and biological functions that are most responsive to the glucocorticoid stimulus in each cell type.

A separate analysis will compare data obtained at the same time point (2 hours or 4 hours) between the high-dose and low-dose groups, to test whether there are significant differences in the transcriptional effect of glucocorticoids at the two doses. Finally, we will identify differences and similarities between the baseline transcriptome and the transcriptional response to glucocorticoids in patients with SLE recruited in this study and in healthy volunteers recruited in our previous study. Since the healthy and the SLE participants come from two different studies, they are not directly comparable in many aspects. Therefore, these results will be derived from the two studies separately and no formal comparison will be made across the two studies. We will present the baseline distribution of gene expression, the distribution of gene expression changes, and the subset of differentially expressed genes. For each cell type, we will generate a list of protein-coding or non-coding transcripts that are shared and a list of transcripts that are different between SLE patients and healthy controls.

Sequencing library preparation and sequencing batches will be carefully designed such that samples from the same participant and cell type are run in the same batch and samples from different participants are evenly distributed across batches. This will keep batch effects to a minimum in the identification of differentially expressed genes. For analyses across different participants, such as comparisons among different cell types, linear regression will be adopted with batch as a regression variable to adjust for batch difference. While prior experience suggests that library preparation is the greatest source of batch-to-batch variation in RNA-seq experiments, if the source of batch effects is unclear or cannot be adequately modeled, then the R package SVA will be used.

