3.1 Description of the Study Design

Potential participants will present to the NIH CC for a screening visit. Objective documentation of the diagnosis of SLE, the specific clinical manifestations, and the level of disease activity will be established. A baseline whole blood sample will be obtained at screening. Each enrolled participant will be randomly assigned to 1 of 2 methylprednisolone dose groups: 1 mg/kg or 250 mg.

All enrolled participants will return for a day-long study visit (“infusion visit”) within 75 days of the screening visit. Following collection of a pre-infusion whole blood sample, participants will receive a single IV dose of methylprednisolone (based on the dose group assignment), infused over 30 minutes. Whole blood samples will then be obtained serially, 2 and 4 hours after the start of infusion.

Participants will be discharged after collection of the 4-hour blood sample, measurement of vital signs, and documentation of any adverse events (AEs). Two follow-up phone calls will be made to document any AEs related to the methylprednisolone. If any AEs that may require treatment are documented on the follow-up phone calls, then participants will be asked to return to the NIH CC’s outpatient clinic for evaluation by the principal investigator.

We propose an adaptive study design, in which we will recruit an initial cohort of 20 participants into each of the 2 dosing groups. After processing the samples from these participants, we will perform differential expression analysis to determine if recruitment of additional participants (up to the accrual ceiling of 100) would affect the biological interpretation of the data. If additional data would be unlikely to change the study outcome, then no further recruitment will be pursued.

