6.2 Glucocorticoid Taper

Given the known toxicity of glucocorticoid therapy, it is standard clinical practice to attempt to reduce the lifetime exposure of patients with SLE to glucocorticoids, by periodically tapering their glucocorticoid to the minimum effective dose. An ideal tapering regimen, or a reliable way to identify patients on chronic glucocorticoid therapy in whom the dose can be tapered, have not been defined. Similarly, the biological changes that take place upon glucocorticoid tapering, or the glucocorticoid-responsive genes that help maintain patients in clinical remission, are very poorly understood. In this protocol, we will enroll patients who are in clinical remission and receiving chronic glucocorticoid treatment. In those patients, a glucocorticoid taper will be performed. These are patients who would be good clinical candidates for tapering their glucocorticoid dose under standard clinical practice. In the setting of this study, the rationale for tapering is two-fold:

- i. Patients in whom the dose of glucocorticoid can be tapered to zero can be studied in the same context as those who were not receiving glucocorticoids prior to the study.
- ii. Patients in whom the dose of glucocorticoid is tapered, but their disease activity increases during the taper, can provide very valuable information. Identifying the genes and molecular pathways that differ between a chronic stable dose, a disease flare at a lower dose, and the subsequent response to a glucocorticoid infusion, can help identify the genes that glucocorticoids regulate chronically to sustain clinical remission.

To maximize the safety of glucocorticoid tapering in this study, enrolled participants will be considered eligible for a glucocorticoid taper if they are on a stable prednisone or prednisone-equivalent dose ≤ 10 mg/day and have not had escalation of other immunosuppressive therapies for SLE, as indicated in inclusion criteria 7 and 8, and in exclusion criterion 4.

The taper will be managed by the clinical staff of the NIAMS Lupus Clinical Trials Unit (LCTU). The LCTU staff are actively involved in the care of patients in the study of the natural history of SLE (94-AR-0066), in which all participants in this study will also be enrolled. The tapering protocol is described in **Error! Not a valid bookmark self-reference..**

Table 1. Glucocorticoid Tapering Protocol

Stable glucocorticoid dose (prednisone-equivalent)	Tapering regimen

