		8 mL: Plasma purification	Plasma banking
		5 mL: Serum	Glucocorticoid panel
		4 mL: Acute care panel	N/A
		3 mL: CBC/diff	N/A

CBC/diff = complete blood count with differential; CPK = creatine kinase; dsDNA = double-stranded DNA; ESR = erythrocyte sedimentation rate; hsCRP = high sensitivity C-reactive protein; IGRA = interferon gamma release assay; LFT = liver function test; N/A = not applicable; NK = natural killer; PBMC = peripheral blood mononuclear cell; PT/PTT = prothrombin/partial thromboplastin time.

a Baseline blood will be collected at screening from all potential participants and will be processed as described even if the participant is determined to not be eligible for the study.

b The purpose of this initial sample will be to assess the level of variation at baseline.

c C3 and C4 complement levels and anti-ds DNA antibodies will only be ordered on the day of infusion in patients whose glucocorticoid taper ended due to clinical evidence of a disease flare.

8 Potential Risks and Benefits

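### The pre- versus post-taper contrast in 15.3 is made within tapered participants only, so a screening-to-infusion shift unrelated to the taper cannot be told apart from a taper effect, although untapered participants give the same two samples

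*Combined protocol and SAP*

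**What the plan says.** Section 15.3 assesses baseline variation in each cell type by "comparing the expression values on the day of the screening visit to the 0-hour (pre-infusion) values on the day of the glucocorticoid infusion". The next sentence turns to tapered participants: "For participants who undergo a glucocorticoid taper, this analysis will contrast the pre- and post-taper patterns of gene expression". No reference group, visit-by-taper term or use of the untapered participants' change is stated there or in section 6.2.

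The untapered participants have the same pair of samples. Footnote a of Table 2 (section 7.1) says "Baseline blood will be collected at screening from all potential participants", and section 3.1 says "All enrolled participants will return for a day-long study visit", at which the pre-infusion sample is drawn. Table 2 allots 60 mL to cell-subset isolation on both occasions. Footnote b gives the use of the screening sample: "The purpose of this initial sample will be to assess the level of variation at baseline".

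Section 6.2 gives two reasons for tapering. Participants tapered to zero "can be studied in the same context as those who were not receiving glucocorticoids prior to the study". For those whose disease activity rises during the taper, the differences between stable dose, flare at a lower dose and infusion response "can help identify the genes that glucocorticoids regulate chronically to sustain clinical remission".

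**The concern.** Within the tapered group, visit and taper status are the same variable: every screening sample is pre-taper and every 0-hour sample is post-taper. A change in expression between visits may come from lower glucocorticoid exposure. It may also come from the day of blood draw and cell isolation, calendar time, or the course of the disease. The contrast cannot separate these.

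Multiplicity adjustment does not help, because it limits chance findings and leaves a real shift with another cause in place. The reading in section 6.2, that the differences point to genes under chronic glucocorticoid control, needs that separation. The untapered pairs would supply part of it and are already planned.

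**Working it through.** **Inputs from the documents**
- Contrast: screening versus 0-hour, within person, tapered participants only (15.3).
- Untapered pairs: available (3.1; Table 2).
- Interval after a completed taper from 10 mg/day (Table 1 and section 6.2): two weekly steps to 5 mg/day and five to zero, so 7 steps. That is 6 x 7 = 42 or 7 x 7 = 49 days, depending on whether the first step falls on day 0 or a week later. Adding about 10 days before the infusion gives about 52 to 59 days.
- Interval for participants in flare at screening: within 7 days of enrollment (6.1.1). For the others the limit is 75 days (3.1).

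**Assumptions, because the documents give no figure:** 8 to 20 tapered participants; a shift unrelated to the taper of 0.3 or 0.5 SD of the within-person change; true taper effect zero.

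**The plan's own paired figure.** Section 15.6 states 90% power at 0.72 SD with n = 20. The normal approximation gives Phi(0.72 x sqrt(20) - 1.960) = 89.6%. The exact two-sided paired t-test gives 86.3%. That figure concerns the infusion comparison; none is stated for the taper contrast, and this point does not depend on it.

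**How often the one-group contrast flags such a gene.** Two-sided paired t-test with n - 1 degrees of freedom and noncentrality d x sqrt(n), where d is the shift in SD:

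| Tapered n | d = 0.3, level 0.05 | d = 0.5, level 0.05 | d = 0.3, level 0.001 | d = 0.5, level 0.001 |
|---|---|---|---|---|
| 8 | 11.4% | 23.2% | 0.4% | 1.0% |
| 12 | 15.8% | 35.3% | 0.7% | 2.6% |
| 16 | 20.3% | 46.5% | 1.1% | 5.2% |
| 20 | 24.7% | 56.5% | 1.7% | 8.7% |

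The 0.05 columns are unadjusted. The Benjamini-Hochberg cutoff for a raw p value is at most 0.05 and depends on the data; 0.001 shows a stricter cutoff. Where there is no shift, the flag rate equals the level itself, so even at 0.001 the shifted gene is flagged at several times the nominal rate. The t-test stands in for the planned DESeq2 analysis to show the mechanism.

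**With the untapered change subtracted.** In 40,000 simulated trials each, with 10 tapered and 30 untapered or 20 and 20, and shifts of 0.25 to 1.0 SD, the difference in change was flagged at the 5% level in 4.8% to 5.2%. This holds only if the shift is the same in both groups.

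**Cost in precision.** With equal variances, the SE ratio against the one-group contrast is sqrt(1 + n_tapered / n_untapered):
- 8 and 20: sqrt(1.4) = 1.18
- 20 and 20: sqrt(2) = 1.41
- 20 and 10: sqrt(3) = 1.73

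With 10 tapered and 30 untapered, the taper effect detectable with 90% power rises from 1.15 to 1.21 SD.

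**The case against.** The other side has a good deal in its favour.

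- **No endpoint rests on it.** The taper contrast is not among the objectives or endpoints. A reader might infer that the primary gene lists or the dose comparison are contaminated. They are not directly affected, since they use the infusion-day samples.
- **No taper gene list is promised.** A reader might infer that drifting genes enter an FDR-selected list of taper genes. Section 15.3 only undertakes to contrast patterns; its FDR selection is described for the post-infusion time points.
- **The remission statement is narrower than it looks.** It covers only participants whose disease activity rises during the taper, and it includes the same-day response to the infusion. A gene that merely drifted between visits has no evident reason to respond to the infusion. This is a partial safeguard, not a control for the change between visits.
- **Some protection exists.** Section 15.3 ensures that "samples from the same participant and cell type are run in the same batch", which deals with library and sequencing batch. The baseline-variation check would show a common shift in untapered participants, but nothing ties that result to the taper contrast. Draw day, isolation day, calendar time and disease course remain.
- **Not everyone waits up to 75 days.** Participants in flare at screening are infused within 7 days. Nor do the documents say that collection conditions differ; the cell-isolation volume is the same at both visits.
- **Untapered participants are an imperfect control.** They are not randomised to taper, differ in treatment, and may differ in disease course and interval.

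These limit the scope of the point and shape the fix. They do not supply the missing contrast.

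**Conclusion.** The point holds for the exploratory taper comparison. As written, section 15.3 cannot separate a taper effect from any other screening-to-infusion change, and it leaves unused a comparator that is already being collected.

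The size cannot be fixed from the documents. The rates of 11-25% (0.3 SD) and 23-56% (0.5 SD) are per-gene illustrations at an unadjusted 5% level, with both the shift and the 8 to 20 tapered participants assumed. They would be lower under Benjamini-Hochberg; at 0.001 they are 0.4-1.7% and 1.0-8.7%. They should not be read as the share of reported taper genes that would be false, because the documents do not say how many genes shift or by how much.

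The correction is worth making because section 6.2 gives the comparison an inferential purpose and the samples are already planned.

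**What to change.** In section 15.3:

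1. Keep the simple pre/post-taper change. Report beside it the tapered-minus-untapered difference in screening-to-0-hour change, for each cell type, from one model with participant, visit and visit-by-taper terms. Apply Benjamini-Hochberg to the interaction.
2. Define the comparators as untapered participants who at screening are not on glucocorticoid and not in flare.
3. Account for the screening-to-infusion interval, by adjustment or by restricting to similar intervals.
4. Analyse tapers ending at zero separately from tapers ending in flare. In the latter, non-flaring comparators cannot remove the effect of the flare, and the text should say so.
5. Label the result exploratory and report the numbers tapered and eligible as comparators.

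The cost is analysis-plan wording; no sample, visit or clinical procedure changes. Intervals widen by a factor of about 1.2 to 1.7, depending on those unknown numbers, and the comparison rests on an untestable assumption that the two non-randomised groups would have changed in parallel without the taper.

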While the mechanisms are diverse, a consistent outcome of glucocorticoid exposure is a significant reprogramming of a cell's transcriptional state.^{17,18} The genomic locations of GR binding have been shown to vary widely across cell types,¹⁹⁻²¹ a phenomenon that is explained at least in part by differences in chromatin accessibility and expression differences of GR cofactors.^{19,22,23} This, in turn, suggests that the transcriptional response to glucocorticoids could vary significantly across cell types. In this context, studies of specific cell populations in the species of interest are necessary to gain a realistic view of the genomic effects of glucocorticoids in any system. Immortalized and tumor-derived cell lines have been valuable tools for the study of the molecular biology of GR signaling. However, their genomic composition and chromatin landscape are known to differ substantially from those of human primary cells. Similarly, complex cell mixtures, such as whole blood and peripheral blood mononuclear cells (PBMCs), have offered an initial glimpse of the genes and pathways affected by a glucocorticoid stimulus in primary human cells,^{17,18} but they are limited in their ability to discern cell-specific effects.

To develop a greater understanding of how pharmacologic doses of glucocorticoids regulate immunity and the extent to which they differentially affect distinct cell subsets, we have studied the genome-wide transcriptional response to glucocorticoids in 9 primary human hematopoietic and non-hematopoietic cell types from healthy human volunteers.²⁴ For each cell type, we performed total RNA-seq before, 2 hours after, and 6 hours after in vitro stimulation with methylprednisolone or vehicle. We found that the number of genes that responded to the glucocorticoid stimulus differed substantially among cell types. In addition, the specific transcripts that responded to the glucocorticoid stimulus were very different in each cell type. Of the 10,665 glucocorticoid-responsive transcripts identified, 5184 (48.6%) were significantly differentially expressed after glucocorticoid treatment in only 1 of the 9 cell types, and only 23 (0.2%) were significantly differentially expressed after treatment in all cell types. In principle, the observed differences in the transcriptional response to glucocorticoids among cell types could

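### The 5% FDR set within each cell type and time point does not carry over to genes called unique to one cell type, and no direct test between cell types is specified

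*Combined protocol and SAP*

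**What the plan says.** Section 15.3 describes a differential expression analysis "comparing each of the two post-infusion time points (2 hours and 4 hours) independently against the baseline". A 5% cutoff on Benjamini-Hochberg (BH) adjusted p values is then used to "select the transcripts that will be considered differentially expressed in each cell type at each time point". The plan describes the adjusted p values as ones "which control for the family-wise false discovery rate (FDR) in the presence of multiple comparisons".

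The cell-type comparison follows directly: "The resulting gene lists will be contrasted to determine, for example, which genes are uniquely differentially expressed in a specific cell type". Section 15.3 gives no time-by-cell-type test, no rule for deciding that a gene does not respond in the other cell types, and no error rate for the resulting set.

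One later sentence in section 15.3 bears on this: "For analyses across different participants, such as comparisons among different cell types, linear regression will be adopted with batch as a regression variable". It sits in the paragraph on sequencing batches and serves to adjust for batch.

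For context, section 1.1 reports that 5184 of the 10,665 responsive transcripts (48.6%) in the earlier in vitro study "were significantly differentially expressed after glucocorticoid treatment in only 1 of the 9 cell types", and that 23 (0.2%) responded in all nine.

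**The concern.** BH at 5% limits the expected share of false calls in a whole list. It gives no such guarantee for a part of the list chosen afterwards by another criterion, and here the criterion is absence from every other list. Two errors follow.

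1. A true response shared by several cell types tends to be called several times and so leaves the unique set. A false call rarely repeats and so stays in it. The false share of the unique set can therefore exceed that of the list it came from.
2. A gene that responds in several cell types but passes the cutoff in only one is labelled unique. Non-significance is read as no response.

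Sections 1.1 and 1.2 make cell-type dependence a central part of the rationale. A reader of the results may well take a unique label at face value and assume that the 5% applies to it. The phrase family-wise false discovery rate adds to that risk: it merges two different error rates and can suggest protection across lists, which the rule does not give.

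**Working it through.** **Plan's own figures.**
- Overlap (section 1.1): 5184/10,665 = 48.6% and 23/10,665 = 0.2%. Both reproduce.
- Power (section 15.6): n = 20 per dose group, 0.72 SD, paired t-test, 90%; two-sided 0.05 assumed. The normal approximation is Φ(0.72 × √20 − 1.96) = Φ(3.22 − 1.96) = 89.6%, which agrees. The exact noncentral t (19 df) gives 86.3%.

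**Missed responses elsewhere.** For the same gene (0.72 SD, n = 20), exact two-sided power falls as the per-gene cutoff tightens:

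| Cutoff | Power |
|---|---|
| p < 0.05 | 86% |
| p < 0.01 | 64% |
| p < 0.001 | 30% |

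A BH adjustment over thousands of transcripts puts the cutoff on the raw p value below 0.05. A gene responding equally in several cell types can therefore easily miss the cutoff in some of them.

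**False calls in the unique set: hand calculation.** Take one list per cell type and a 5% FDR in the earlier study (both assumed; section 1.1 does not state its cutoff).
- Genes in two to eight lists: 10,665 − 5184 − 23 = 5458.
- Fewest list entries: 5184 + 2 × 5458 + 9 × 23 = 16,307.
- Most list entries: 5184 + 8 × 5458 + 9 × 23 = 49,055.
- False calls at 5%: 815 to 2453.
- If every false call appeared in one list only: 815/5184 = 15.7%, to 2453/5184 = 47.3%.
- With a realised list FDR of about 4.4% and about 75% of false calls in one list only (both close to the simulation medians below): 16,307 × 0.044 × 0.75 = 538, or 10%, to 49,055 × 0.044 × 0.75 = 1619, or 31%.

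These are rough brackets. The documents do not say how the 5458 genes spread over two to eight lists.

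**False calls in the unique set: simulation.** Paired t-tests with n = 20 and BH at 5% in each cell type. Assumed: 7 cell types (the number named in the Précis) or 9, 15,000 or 25,000 transcripts, independent errors between cell types, and varied effect sizes and sharing patterns. Only scenarios near the reported overlap were kept (44-53% of called genes unique, under 1% called in all cell types).

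| | 7 cell types | 9 cell types |
|---|---|---|
| Unique genes with no true effect in that cell type, median (range) | 14% (6.5-18%) | 14% (7-23%) |
| Unique labels wrong for either reason, median | 38% | 52% |

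Across both columns, the FDR of the lists themselves stayed at 3.6-5.1%, as intended. Of all false calls, 44-95% fell in the unique set (medians 76-79%). Unique labels wrong for either reason ranged from 16% to 74%.

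**Sensitivity.**
- Correlated errors between cell types of one participant: in a separate simulation near the same overlap, the false share was 12-16% with correlation from 0 to 0.5, and a further 25-27% of unique genes truly responded in another cell type.
- Little or no sharing of true responses: false share 1.7-4.6%.
- Heavy sharing, beyond what section 1.1 reports: 35-71%.

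**The case against.** Much of the case on the other side is fair.

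- The primary endpoint is the list for each cell type and dose, and BH within each list suits it. The unique contrast is introduced only as an example and is not itself an endpoint. This stands.
- No passage says that candidate targets will be drawn from the unique set. The lists themselves go to pathway enrichment, and functional validation of targets is a secondary endpoint. This stands too, although validation spends effort on any false leads that reach it.
- A reader might infer that the error rate of the unique set is several times 5% as a matter of fact, or that the counts in section 1.1 prove a minimum number of false genes. The documents support neither. The multiple depends on overlap: at the reported overlap it runs from about 1.3 (6.5%/5%) to about 4.7 (23%/5%), and with little sharing there is no excess. The counts give no floor, because some false calls do repeat. They also come from in vitro work in healthy volunteers, with a cutoff the protocol does not state.
- A reader might also infer that the unique set is the least reliable output of the trial, or that the plan attaches a 5% FDR label to it. The plan makes no such statement, and nothing here compares that set with the other outputs.
- The regression for comparisons among cell types could be read as the missing test. It would answer the point if it contained a time-by-cell-type contrast tied to the unique calls. As written it is a batch adjustment, so this does not stand.
- Family-wise is loose wording: the same section names BH and applies the cutoff per cell type and time point. It merits a correction and nothing more.

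**Conclusion.** The concern holds as a gap in error control for one family of downstream claims, with a conditional size. Following section 15.3 as written yields a set of unique genes for which 5% is not controlled and in which non-significance elsewhere is treated as no response.

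At roughly the in vitro overlap, about 7-23% of that set would be false in their own cell type, and a further substantial share (about a quarter in one simulation) would truly respond in another cell type. With almost no sharing, the false share is at or below 5%.

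The figures assume that the in vitro overlap carries over to patients with SLE in vivo, and they rest on assumed transcript numbers, effect sizes and sharing patterns. Moderate correlation between cell types did not remove the problem. The per-cell-type lists are unaffected.

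**What to change.** Keep the per-cell-type lists at 5% FDR as the primary endpoint, and change section 15.3 as follows.

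1. Base claims of cell-type specificity on a direct test of the time-by-cell-type difference. The model must keep the before/after pairing within participant and cell type, which requires a participant-by-cell-type term and not only a participant term.
2. Call a gene cell-type-specific only if it responds in that cell type and its change differs from that in the other cell types, with BH at 5% over that set of tests. State the exact contrast in advance. In simulation, testing the difference directly kept calls that were false in their own cell type at or below 3%.
3. Describe such genes as responding differently, not uniquely. A gene that responds everywhere but more strongly in one cell type would also pass this test.
4. Label any result from list overlap, unique or shared, as descriptive, with no 5% FDR claim. Do not replace the shared lists by BH on the largest p value across cell types: that yields a subset of the intersection of the separate lists and so misses even more shared genes.
5. Replace the family-wise wording with false discovery rate within each list, and say how the batch regression relates to the new test.

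The cost is SAP wording and some extra analysis work, with no new samples or visits. The set of genes called specific will differ and may be shorter.
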